## **2.1 Name and Description of Investigational Product or Intervention**

*Proactive outreach.* Will consist of outreach calls with the offer of a connection to counseling.

Outreach calls. Consistent with a chronic care approach, proactive outreach will be conducted by the tobacco treatment case manager. Outreach will follow the 5 A's approach. The aims of the outreach are to: (1) increase motivation to stop or reduce smoking, (2) improve self-efficacy, (3) facilitate participation in evidence-based treatment. Participants will be offered mental health tailored tobacco cessation counseling delivered by the case manager or connection to local tobacco cessation programs. In addition, the case manager will discuss tobacco cessation medication options and coordinate with the participants' prescriber and case manager to facilitate receipt of medication.

Counseling. The counseling protocol is tailored to psychiatric patients. Up to 7 counseling sessions per round of counseling will be offered using a motivational interviewing style to enhance motivation and cognitive behavioral therapy skills. Counseling will be conducted by phone, secure video visit, or in person (participant preference).

*Provider intervention* will include every provider administering the 5A's at every visit. Patients who are interested in cessation support will be referred to the tobacco treatment case manager for behavioral treatment and, if the provider can prescribe, be offered a prescription for tobacco cessation pharmacotherapy.

## **2.2 Findings from Non-Clinical and Clinical Studies**

N/A

## **2.3 Selection of Drugs and Dosages**

N/A

## **2.4 Relevant References**

## **2.5 Compliance Statement**

This study will be conducted in full accordance of all applicable Hennepin Healthcare Research Policies and Procedures and all applicable Federal and State laws and regulations. All episodes of noncompliance will be documented and reported according to the Prompt Reporting Guidelines, Attachment EEE, of the Hennepin Healthcare IRB Policies and Procedures.

The investigators will perform the study in accordance with this protocol, will obtain consent and assent, unless waiver of consent or other alteration is approved, and will report unanticipated problems involving risks to subjects or others and SAEs in accordance with The Hennepin Healthcare IRB Policies and Procedures and all Federal requirements. Collection, recording, and reporting of data will be accurate and will ensure the privacy, health, and welfare of research subjects during and after the study.

### 3 STUDY OBJECTIVES

The overall purpose of this study is to develop an implementation strategy for a proactive tobacco cessation intervention.

Aim 1: Adapt an evidence-based implementation strategy to CMHCs.

Aim 2: Pilot test the implementation strategy

Aim 3: Conduct a pilot trial to assess the feasibility, acceptability and initial effectiveness of both the implementation and intervention strategies.

### 4 INVESTIGATIONAL PLAN

#### 4.1 General Schema of Study Design

Study 1 is a qualitative interview study to help assess the needs of community mental health centers in terms of tobacco cessation and to get feedback on proposed study materials/design.

Study 2: Is a pre-post pilot trial with the main aim to test the feasibility and acceptability of study procedures.

Study 3: is a pilot trial to test the feasibility, acceptability, and preliminary effectiveness of the intervention and implementation strategies.

##### 4.1.1 Screening Phase and Baseline Assessment

Study 1: CMHC staff. Staff will be recruited during staff meetings, and from informational emails from medical directors. Directors will give the study a list of staff members who are willing to participate. Study staff will call and obtain verbal informed consent. CMHC patients. Case managers will review a list of potential patient participants (identified via chart review). Case managers will give a study flyer to participants who qualify and interested patients will contact the study. Study staff will call interested patients to schedule an in person interview at the community mental health center or a phone interview. Prior to the interview interview, we will obtain written or online, informed consent and conduct the interview. Interviews will be audio recorded.

Studies 2&3: leaders from each community mental health center have agreed to participate. These leaders will provide deidentified administrative data describing each organization. Providers who are interested in participating in the training will be recruited during provider meetings and informal emails from medical directors. Prior to the training, providers will receive a study fact sheet and a baseline survey. Completion of the survey and/or attending the trainings and/or coaching calls will be considered consent to participate. Patients will be given a flyer about the study or will receive a letter introducing the study with the opportunity to opt out. Patients will be contacted by a study staff member to assess interest and, if interested, complete written or electronic, informed consent and the baseline survey.

##### 4.1.2 Study Intervention

Study 1: There is no intervention. This is a qualitative study only.

Study 2: The organization will participate in an implementation intervention, 6 months in duration, that consists of an in-person, hands-on training workshop, performance feedback based on anonymous patient surveys and/or electronic mental record data, and coaching calls. Organizational leaders will also participate in a series of planning meetings. Study staff will work with site leadership to develop templated language for documentation of the 5 A's in the electronic health record. Providers will be given handouts on smoking cessation resources, smoking cessation medications, and a tool to help guide them through the 5 A's. The workshop will cover the importance on intervening with people with serious mental illness about smoking in mental health treatment

settings, available treatments, documentation, and how to do the 5 As. We will make arrangements for lunch to be provided during the workshop.

The patient intervention will consist of providers discussing tobacco with patients during their visits using the “5 A’s” to ask the patient about their tobacco use, advise tobacco users to quit, assess readiness to quit, assist patient in quitting by providing counseling, medication, or a referral, and arranging for follow-up. In addition, 25 patients who consented to the study will receive outreach to discuss their tobacco use and offer to help them obtain smoking cessation medication through their existing providers and also to provide ongoing counseling (up to 7 counseling sessions by phone, secure video, or in person). Outreach may also be done in person in the context of routine clinical care if the participant prefers it.

Study 3: The organizational intervention is the same as in study 2, except the implementation support will last for 9 months, and leaders will participate in a sustainment meeting at the end of the implementation to form a plan to sustain the intervention once implementation support is removed.

The patient intervention is the same except that 50 patients will receive 3 outreach attempts, over 9 months, each with an invitation to help the patient connect with treatment.

#### **4.1.3 Part 2 (Use an appropriate descriptor such as “Open-Label Treatment”)**

All participants will receive the study interventions.

#### **4.1.4 Follow-up**

Study 1: there is no follow-up.

Study 2: Provider behavior will be monitored for 3 months via anonymous patient surveys and/or via electronic mental record review. 5-6 CMHC staff members will participate in qualitative interviews at the end of the implementation period (6 months post implementation). Interviews will be audio recorded.

Patients will complete one follow-up survey, 3 months post-enrollment. Abstinent participants will also complete a CO reading. This may be done during a visit to the clinic, a home visit, or via a mailed CO device. 5-6 participants will also participate in qualitative interviews. Interviews will be audio recorded.

Study 3: Provider behavior will be monitored monthly via anonymous patient surveys and/or through medical record review. Patients will be followed at 3, 6, 9, and 15 months post-implementation launch. 5-6 patients and 5-6 CMHC staff will also participate in qualitative interviews. Interviews will be audio recorded.

### **4.2 Allocation to Groups and Blinding**

N/a

### **4.3 Study Duration, Enrollment and Number of Sites**

#### **4.3.1 Duration of Study Participation**

Study 1: participation is 1 day

Study 2: CMHC staff will participate for 6 months, patients will participate for 3 months

Study 3: CMHC staff will participate for 12 months, patients will participate for 15 months.

#### **4.3.2 Total Number of Study Sites/Total Number of Subjects Projected**

Study 1: Study procedures will be conducted by Hennepin Healthcare Research Institute staff, but will recruit from 2 community mental health centers (Central Minnesota Mental Health Center and Lee Carlson Center).

Study 2: Study procedures will be conducted by Hennepin Healthcare Research Institute staff and two staff members from Lee Carlson Center.

Study 3: Study procedures will be conducted by Hennepin Healthcare Research Institute staff and two staff members from Central Minnesota Mental Health Center.

## **4.4 Study Population**

### **4.4.1 Use of Vulnerable Populations and Patients Who Opt Out of Research**

We are recruiting patients at community mental health centers because these patients have a very high tobacco use rate and a very high incidence of tobacco-related mortality. We will exclude people who are decisionally impaired by first having their treatment providers determine if they are able to provide consent for a research study and also by verifying that the patients understand the consent form by asking them several questions about what they have read in the consent form before allowing them to consent. Of note, just because a patient has a documented mental illness does not necessarily mean that they are decisionally impaired. Many people living with mental illness live independently and make their own legal and healthcare decisions.

## **3.5 Inclusion and Exclusion Criteria**

### **3.5.1 Inclusion Criteria**

Inclusion criteria for patients: daily cigarettes smokers (smoking >25 days/month), English speaking, patient in one of the two community mental health center study sites. Inclusion criteria for providers/staff: must be staff member at one of the community mental health center study sites.

### **3.5.2 Exclusion Criteria**

Exclusion criteria for patients: cognitive impairment, judged by community mental health center staff as unable to participate in research, no access to a telephone, no address at which they can receive mail. There are no exclusion criteria for providers

## **5 STUDY PROCEDURES**

### **5.1 Screening Visit and Baseline Assessment**

Study 1: CMHC staff will be recruited during provider meetings, and from informational emails from medical directors. Directors will give the study a list of providers who are interested. Study staff will call and obtain verbal informed consent. We will ask the case managers to review a list of potential patient participants (based on chart review). CMHC Patients. Case managers will inform the study team whether patients would be able to participate in stakeholder interviews. Case managers will give out flyers to eligible patients. Eligible patients will contact the study to schedule an in-person interview at the community mental health center, or a phone interview. Written or online, informed consent will be obtained prior to the interview. If the patient is unable to come to an in person visit, we will mail the informed consent form to the patient with a self-addressed, stamped envelope or email or text them a link to the REDCap consent form. When we call the patient for their interview, study staff will go through the consent form with the patient using a script. The patient will take a quiz on what they have read. If the patient would like to use paper consent, we will ask them to take a picture of the signed consent form page and text or email it to study staff prior to the interview. We will then ask them to mail the signed consent form back to the research team in a self-addressed, stamped envelope provided. If the patient chooses to complete consent online, they will digitally sign in REDCap.

Study 2: Studies 2&3: leaders from each community mental health center have agreed to participate. These leaders will provide deidentified administrative data describing each organization. Providers who are interested in participating in the training will be recruited during provider meetings and informal emails from medical

directors. Providers will be given a fact sheet and told that if they complete the survey, participate in trainings or coaching calls, that they will be considered to have consented to that activity. Patients will be given a flyer about the study, or mailed a letter and a flyer and patients who receive the letter/flyer will be contacted by the smoking cessation case manager or other study staff member to assess interest and, if interested will schedule a phone, video visit, or in person visit to complete written or electronic, informed consent and the baseline survey via redcap or paper (patient preference).

## 5.2 Study Intervention

Study 1 does not have an intervention.

Studies 2 & 3 have an implementation strategy for providers and an intervention delivered by clinic staff directly to the patients.

Studies 2 & 3:

### Implementation strategy for the health system:

The organization will participate in an implementation intervention, 3 months in duration for study 2 and 9 months in duration for study 3, that consists of a hands-on virtual or in person training workshop, performance feedback based on anonymous patient surveys given once/month and/or aggregate electronic medical record data, and coaching calls. The workshop will be video recorded and will be available to providers to watch following the training if they could not attend due to scheduling, or if they want to refer back to the workshop. Organizational leaders will also participate in planning meetings (study 2 & 3) and an end of study sustainment meeting (study 3). Study staff will work with site leadership to develop templated language for documentation of the 5 A's. Providers will be given handouts on smoking cessation resources, smoking cessation medications, and a tool to help guide them through the 5 A's. The workshop will cover the importance on intervening with people with serious mental illness about smoking in mental health treatment settings, available treatments, documentation, and how to do the 5 As.

### Patient intervention:

*Proactive outreach.* Will consist of outreach attempts with the offer of a connection to counseling.

Outreach calls. Consistent with a chronic care approach, proactive outreach will be conducted by the tobacco treatment case manager. In study 2, the case manager will make one outreach call per participant. These outreach attempts may be conducted via telephone, HIPAA secure video calls, or at an in person visit (participant preference). Each outreach attempt will include five call attempts per available telephone number. In addition, if the participant agrees to receive texts, the participant will receive up to 5 outreach text messages. If the participant is in active clinical care, the tobacco cessation case manager can also offer to see the participant in person following a regularly scheduled appointment to discuss their smoking. In study 3, the case manager will make 3 outreach attempts, each 3 months apart. The aims of the outreach are to: (1) increase motivation to stop or reduce smoking, (2) improve self-efficacy, (3) facilitate participation in evidence-based treatment. Participants will be offered mental health tailored tobacco cessation counseling delivered by the case manager or connection to local tobacco cessation programs. In addition, the case manager will discuss tobacco cessation medication options and coordinate with the participants' prescriber and case manager to facilitate receipt of medication.

Counseling. The counseling protocol is tailored to psychiatric patients. Participants will engage in up to 7 counseling sessions using a motivational interviewing style to enhance motivation and cognitive behavioral therapy skills. Counseling sessions will be timed based on the participant's readiness to quit, such that more sessions will take place surrounding quit dates. Counseling will be done by phone, secure video visit, or in person (participant preference).

*Provider intervention* will include every provider administering the 5A's at diagnostic assessment and treatment planning visits. Patients who are interested in cessation support will be referred to the tobacco treatment case manager for behavioral treatment and, if the provider can prescribe, be offered a prescription for tobacco cessation pharmacotherapy.

### **5.2.1 Study procedures and visits study 1**

Study 1: Patients will provide written or online, informed consent prior to the interview and complete the interview in person or by phone. CMHC staff will be given the option of participating by phone or in person and will therefore provide oral consent. Interviews will take 30-60 minutes.

### **4.2.2 Study Procedures and visits study 2**

#### **Patients.**

Enrollment. Patients will provide written, or online, informed consent. They will then complete a baseline survey. Following the baseline survey, they will be called and texted for an outreach call, conducted by a smoking cessation case manager, on staff at the community mental health center. If participants prefer, the outreach session can be conducted via secure video visit or in person. At the outreach session, they can elect to enroll in smoking cessation counseling and/or get help from the case manager to reach out to their providers to obtain smoking cessation medication.

Follow-up. Three months post-baseline, patients will complete a follow-up survey online or by phone. Participants reporting abstinence will complete an expired breath CO test either conducted with a portable CO monitor mailed to the participant, a home visit, or an in-person clinic visit. At the end of the study, 5-6 patients will be selected to complete a qualitative interview.

#### **Providers.**

Training. Providers will receive a study fact sheet and baseline survey prior to the trainings. Completion of the baseline survey or attendance at the trainings will be considered consent to participate. Providers will complete a recorded, online training via Zoom or an in-person training regarding providing smoking cessation interventions to patients. This training will be attended by investigators from Brown University ([name], [name]) who will edit training videos for future site use. An IAA will be obtained before Brown investigators participates in research activities. Providers will then have the opportunity to participate in coaching calls for 3 months. Providers will receive monthly performance feedback about smoking cessation interventions from anonymous patient surveys or aggregate medical record data for 3 months in study 2 and 9 months in study 3. Leadership for the organizations have already agreed to participate. Leaders will participate in a readiness meeting at the beginning of the study (study 2 and 3), and a sustainment visit at the end of the implementation period (study 3 only). We will work with the site to create the following implementation tools: handouts about community smoking cessation resources, handouts about smoking cessation medications, decision aids to complete the 5 As, templated language to put in electronic health record notes.

Assessment. Providers will complete a readiness assessment before and after the in-person training. We will also assess provider performance from brief, anonymous patients after visit surveys or aggregate electronic medical record data. In patient surveys, beginning the month prior to implementation, the community organization will add study surveys to their pre-existing after-visit surveys electronically about whether their provider completed each of the 5 A's (ask, advise, assess, assist, & arrange). At the end of the study, 5-6 providers will be selected to complete a qualitative interview.

### **4.2.3 Study procedures and visits study 3**

#### **Patients.**

Enrollment. Patients will provide written or electronic, informed consent. They will then complete a baseline survey. At the time of the provider training, they will complete a second baseline survey. Following the second baseline survey, the smoking cessation case manager will begin an outreach attempt (phone, text, or in person). During the outreach, they can elect to enroll in smoking cessation counseling and/or get help from the case manager to reach out to their providers to obtain smoking cessation medication. Outreach attempts will be repeated at 3 months, and 6 months following the second baseline survey.

Follow-up. Participants will complete additional follow-up surveys at 3, 6, and 12 months following the second baseline survey. Follow-up surveys will be completed by phone or via an online survey. Participants who report abstinence at the 12-month follow-up will be asked to complete a mailed or in-person CO test. 5-6 patients will participate in a qualitative interview.

Providers will receive a study fact sheet and baseline survey prior to the trainings. Completion of the baseline survey or attendance at the trainings or coaching calls will be considered consent to participate. Providers will complete a recorded, online training via Zoom or an in-person training regarding providing smoking cessation interventions to patients. This training will be attended by investigators from Brown University ([name], [name]) who will edit training videos for future site use. Providers will then have the opportunity to participate in coaching calls for 9 months. Providers will receive performance feedback about smoking cessation interventions from patient surveys or electronic health record data starting at the second baseline through 9 months post implementation. Leadership for the organizations have already agreed to participate. Leaders will participate in a virtual or in person site visit at the beginning of the study. 5-6 employees will participate in a qualitative interview. We will work with the site to create the following implementation tools: handouts about community smoking cessation resources, handouts about smoking cessation medications, decision aids to complete the 5 As, templated language to put in electronic health record notes.

### **5.3 Concomitant Medication**

N/A

### **5.4 Rescue Medication Administration**

N/A

### **5.5 Subject Completion/Withdrawal**

Subjects may withdraw from the study at any time without prejudice to their care or their employment. They may also be discontinued from the study at the discretion of the Investigator for lack of adherence to study treatment or visit schedules, and AEs. The Investigator or the Sponsor may also withdraw subjects who violate the study plan, or to protect the subject for reasons of safety or for administrative reasons. It will be documented whether or not each subject completes the clinical study. If the Investigator becomes aware of any serious, related adverse events after the subject completes or withdraws from the study, they will be recorded in the source documents and on the CRF.

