Subject Population Key Criteria for Inclusion and Exclusion:	Participants will be patients and employees (leadership and clinical staff) at two community mental health centers in Minnesota. Inclusion criteria for employees are to be on staff at the two community mental health center recruitment sites. There are no exclusion criteria for employees. Patient inclusion criteria include being English-speaking, current smokers (>25 days/month), patients at the community mental health center. Patient exclusion criteria includes judged by community mental health as being unable to participate in research (due to cognitive impairment or any other reason), no access to a telephone, no access to an address at which they can receive mail.
Number Of Subjects	Total Number of Subjects: Study 1: 29; Study 2: 25 patients, 33 staff; study 3: 50 patients, 200 staff Total Number at Hennepin Healthcare: 0 Total Number of Sites: 2
Study Duration	For study 1, each subject's participation will last one day, the entire study will last 3 months For study 2, each patient subject's participation will last 3 months, staff participation will last 6 months, the entire study will last 6 months For study 3, each patient subject's participation will last 15 months, staff participation will last 12 months, the entire study will last 18 months
Study Phases Screening Intervention Follow-Up	Study 1 potential participants will be approached for a single time point consent and qualitative interview. Study 2 potential patient participants will be approached in person or via an information letter, interested participants will complete informed consent and a baseline survey, all participants will receive and outreach attempt and may choose to enroll in counseling, participants will complete a follow-up survey 3 months post-enrollment. Some participants will be selected to participate in qualitative interviews. Study 3: potential participants will be approached, interested participants will complete informed consent and a baseline survey. 3 months later, participants will complete a second baseline survey. Participants will receive 3 outreach attempts, 3 months apart. At each outreach, participants will be given the choice of whether to enroll in counseling. Participants will complete follow-up surveys at 6, 9, and 15 months post enrollment.

---

---

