#### **5.5.1 Early Termination Study Visit**

N/A

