## 6.2 Efficacy Evaluations

Feasibility will be measured by the percent of providers who: attend the online and in person trainings, complete role plays, attend coaching calls, and receive performance feedback. We expect the majority (>75%) of providers and leaders to attend the trainings and receive performance feedback. For patients, feasibility will be measured by the proportion of patients who enroll in the study, the proportion who accept a proactive outreach and the proportion who complete the follow-up. Previous studies (preliminary studies 1-3) using this recruitment strategy have yielded a 30-44% response rate to the enrollment invitations, 62-71% for the proactive call, and 66-74% for follow-up assessment. Results in this range would be considered feasible.

Acceptability. Patients will complete the 8-item Client Satisfaction Questionnaire (CSQ) during the follow-up assessment. Qualitative interviews with 5-6 patients and 5-6 providers will be conducted at the 3-month follow-up (study 2), and 15 month follow-up (study 3). Interviews will be conducted by a trained research staff member. Interviews will contain open ended questions about treatment (for patients) and implementation (for providers and leaders) acceptability, burden, and suggestions for improvement.

Effectiveness. Implementation Effectiveness will be evaluated by the proportion of patients who receive the 5As and the proportion who report using smoking cessation counseling and medication measured 3-months after the start of the implementation period (study 2) and at 3, 6, and 12 months post baseline 2 (study 3) assessed via patient report. Patient Effectiveness will be measured by carbon monoxide (CO)-confirmed 7-day point-prevalence from tobacco post-intervention (3 months for study 2 and 12 months from second baseline for study 3). Secondary patient outcomes will include: 30-day point-prevalence abstinence, the number of self-reported ≥24 hour quit attempts and reductions in smoking via cigarettes per day.

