# 7 STATISTICAL CONSIDERATIONS

Qualitative analysis. Using a structured debriefing form, post-interviews notes will be written at the end of each interview and reviewed by all co-investigators. Interviews will be transcribed and deidentified. Transcription will be completed by Landmark Associates Inc. We will develop analytical codes using an iterative method in which interview notes are reviewed to: 1) consider whether the qualitative agenda is appropriate and complete, and 2) develop an initial coding structure. Deductive codes will be drawn from the interview questions (e.g., treatment needs); review of the interview notes will also allow the creation of inductive codes which capture emergent concepts from the interviews. Investigators and trained study staff will code the transcripts. Each transcript will be independently coded by two coders, who will meet to resolve discrepancies. Final codes will be entered into NVivo qualitative data analysis software. We will conduct a framework matrix analysis to identify the most effective ways to organize the content and logistics of implementation strategy and pilot study design and will help guide our pilot study protocol.

Quantitative Analysis. As a preliminary step, CMHC, provider, and patient-level characteristics will be summarized at baseline. Differences between CMHC's will be tested using graphical methods, non-parametric, and parametric tests as appropriate (e.g., Wilcoxon rank-sum test for skewed data, t-tests for normally distributed continuous data & chi-squared tests for categorical data). Consistent with Aim 3, feasibility and acceptability will be assessed as follows: feasibility will be measured by the percent of providers who attend the online and in person trainings, complete role plays, and receive performance feedback. Implementation will be considered feasible if at least 75% of providers and leaders attend the trainings and receive

performance feedback. For patients, feasibility will be measured by the proportion of patients who enroll in the study, the proportion who accept a proactive outreach and the proportion who complete the follow-up. The study will be considered feasible if results are in the range of those found in preliminary studies: 30-44% response rate to the enrollment invitations, 62-71% for the proactive call, and 66-74% for follow-up assessment (See Preliminary Studies Section).

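### Section 5.5 lets the investigator discontinue patients from the study for non-adherence, although adherence is itself a feasibility outcome, and nothing in section 7 protects the abstinence, satisfaction and feasibility results from that loss.

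*Combined protocol and SAP*

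**What the plan says.** Section 5.5 on withdrawal leaves it to the investigator whether to discontinue a patient "for lack of adherence to study treatment or visit schedules". The discontinuation is from the study, not only from the intervention. The same section requires a record for every patient: "It will be documented whether or not each subject completes the clinical study". Section 5.5.1, "Early Termination Study Visit", is marked not applicable. The only information that 5.5 provides for after a patient leaves is on serious related adverse events that come to the investigator's notice.

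Uptake is voluntary. The synopsis says of study 3: "At each outreach, participants will be given the choice of whether to enroll in counseling". Neither 5.5 nor any other section defines lack of adherence to study treatment.

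Uptake and retention are also outcomes. Besides enrollment, section 7 measures patient feasibility by "the proportion who accept a proactive outreach and the proportion who complete the follow-up", and it calls the study feasible if results fall in the ranges of the preliminary studies: "62-71% for the proactive call, and 66-74% for follow-up assessment". Section 6.2 defines patient effectiveness as "carbon monoxide (CO)-confirmed 7-day point-prevalence from tobacco post-intervention", at 3 months in study 2 and 12 months after the second baseline in study 3. The satisfaction questionnaire is completed at follow-up, and section 7 sets its criterion at 80% or more of participants at least somewhat satisfied.

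**The concern.** In this trial, not answering outreach and not completing a survey are results. A rule that lets such patients be discontinued from the study makes the end of follow-up depend on the behaviour under study.

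Three things are at stake:

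- **Abstinence and satisfaction.** Patients who do not engage are plausibly more likely to be still smoking and less satisfied. Once they are out of the study, no later survey or CO reading is planned for them. A mixed model fitted to the data in hand does not repair loss that depends on unobserved smoking status.
- **The study 3 intervention.** The plan is for three outreach attempts, 3 months apart, on the reasoning that repeated invitation reaches people who did not respond before. Discontinuing a non-responder after the first attempt removes the kind of patient whom the later attempts are meant to reach.
- **The feasibility verdict.** If discontinued patients also leave the denominator, a rate below the feasible range can move into it.

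**Working it through.** **Does the plan guard against this?** The relevant places, side by side:

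| Place | What it settles | What it leaves open |
|---|---|---|
| 5.5 | Completion status is recorded for each patient | Whether discontinued patients are still surveyed |
| 5.5.1 | No early termination visit | No final outcome is collected on leaving |
| 7, feasibility | Which proportions, and the target ranges | The denominator |
| 7, effectiveness | Generalized linear mixed models | The analysis set and how missing abstinence counts |
| 7.1.1 | All entered subjects are analysed | Applies to safety only |
| 9.2 | Missing data are to be kept to a minimum | Any rule for analysing them |

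No passage keeps discontinued patients in follow-up or in the efficacy denominators. Equally, no passage removes them.

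**The plan's own ranges as counts.** With 50 patients (section 7.2):

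- Outreach: 0.62 × 50 = 31 to 0.71 × 50 = 35.5 acceptors.
- Follow-up: 0.66 × 50 = 33 to 0.74 × 50 = 37 completers.

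The plan gives no expected number of discontinuations and no target abstinence rate. The counts below are therefore assumptions.

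**Feasibility, if discontinued patients leave the denominator.** The rate becomes x/(50 − d), where x is the number of successes and d the number discontinued, none of them among the successes.

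- Follow-up, x = 28: 28/50 = 56.0%, below 66-74%. To reach 66% requires 50 − d ≤ 28/0.66 = 42.4, so d = 8. Then 28/42 = 66.7%, inside the range.
- Outreach, x = 28: 28/50 = 56.0%, below 62-71%. To reach 62% requires 50 − d ≤ 28/0.62 = 45.2, so d = 5. Then 28/45 = 62.2%, inside the range.
- In general, dropping 5 to 10 patients multiplies a rate by 50/45 = 1.11 to 50/40 = 1.25.

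**Feasibility, if all enrolled stay in the denominator.** There is no upward shift. If 33 patients would have completed and 3 of them were discontinued instead, the rate falls from 33/50 = 66% to 30/50 = 60%. The direction of the effect thus depends on a denominator that section 7 does not state.

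**Abstinence.** Assume 5 quitters, none discontinued, and every discontinued patient still smoking.

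- All enrolled: 5/50 = 10.0%.
- 5 discontinued and omitted: 5/45 = 11.1%.
- 10 discontinued and omitted: 5/40 = 12.5%.

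For scale, analysing only the 33 to 37 patients followed up, whatever the cause of loss, gives 5/37 = 13.5% to 5/33 = 15.2%. Discontinuation for non-adherence would be one part of that wider loss.

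**The case against.** The strongest case on the other side has five parts.

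1. **The rule is permissive.** The investigator may use it, and may never do so. A reader might infer that 5.5 removes the failures from the results. The documents do not support that: no section takes a discontinued patient out of a denominator, and on the ordinary reading such a patient is a non-completer, which lowers the follow-up rate. This stands.
2. **Declining is not shown to be non-adherence.** A reader might take the 62-71% acceptance range to mean that 14 to 19 of 50 patients could be discontinued, since 50 × (1 − 0.71) = 14.5 and 50 × (1 − 0.62) = 19. But the plan treats that level of non-acceptance as feasible, and nothing equates it with lack of adherence. A refusal is also observed before any discontinuation, so the rule does not erase it. This stands; what remains is that the term is undefined.
3. **Some of these patients would be lost anyway.** Where a discontinued patient would never have answered, the rule costs no data, and any inflation comes from the denominator alone. This stands, and it is why the size cannot be attributed to 5.5 by itself.
4. **There is oversight.** Completion status is recorded. Under 9.4.1 the DSMB reviews the rules for discontinuation before launch, and drop-outs with their reasons during enrollment. This makes selective discontinuation visible. It neither keeps patients in follow-up nor sets an analysis rule.
5. **The stakes are limited.** These are single-group pre-post pilots, and the adjusted effects are exploratory. That is fair, but the feasibility ranges are stated criteria and the abstinence estimate will inform later work.

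**Conclusion.** The concern holds in a limited form. Section 5.5 permits loss that depends on the outcome, and the plan does not prevent it. The effect on abstinence and satisfaction is direct: ending study participation stops collection of data that might still have been obtained, from patients likely to be unfavourable cases. The effect on feasibility is conditional. Rates rise only if discontinued patients also leave the denominator, and fall or stay the same if all enrolled are counted.

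Under the first condition, 5 to 8 discontinuations among 50 would be enough to move an assumed 56% into the stated feasible ranges, and an assumed 10% abstinence would read as 11.1% to 12.5% with 5 to 10 patients omitted. These counts are illustrations, not forecasts. They rest on assumed successes and discontinuations, and on no success being among those discontinued. The documents do not support saying that the rule will be used often, or that it removes failures automatically. The change is worth making before the data are analysed, because it is specific and cheap.

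**What to change.** - **Section 5.5.** State that non-adherence to treatment or to the visit schedule is not a ground for ending outcome data collection. Such patients stay in all scheduled survey attempts unless they withdraw consent or are withdrawn for the safety, adverse-event or administrative reasons already listed. Make clear that non-adherence alone is not to be handled as a violation of the study plan, which 5.5 also lists as a ground. Define lack of adherence to study treatment, given that counseling is optional.
- **Section 7.** Use all enrolled patients as the denominator for outreach acceptance, follow-up completion and abstinence. State how a missing abstinence result counts, with a sensitivity analysis. Report investigator discontinuations separately, with number, timing and reason.

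This concerns outcome data collection and analysis only. It leaves decisions about care, and the safety withdrawals, as they are. The cost is a few sentences in two sections and continued survey attempts for any patients concerned. The downside is that rates may look slightly less favourable.
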